Mobile Mental Health Apps for Suicide Prevention

NCT number: NCT04536935

Document Date: 08/21/2020

Purpose. Access to mental health care by essential workers and the unemployed during the COVID19 pandemic has been challenging. Usual access to mental health care is limited by social distancing, and for many now unemployed due to closures of businesses, insurance is insufficient to cover the costs of mental health care. For these individuals who are at risk for suicide (isolation, unemployment, financial crisis plus past suicide attempts, significant mental health challenges), access to care is crucial and many maybe turning to online and accessible interventions, such as mental health apps and other online resources. Indeed, organizations such as the VA have already created free access mobile applications for mental health in anticipation of this need. Using Psyberguide, we will identify the top ten free apps that address mental health issues and conduct a nation-wide evaluation of these apps with participants who are essential workers and unemployed with risk for suicide. Participants will first be surveyed about which strategies they have used to manage mental health issues, what apps and online tools they have used, and what usability challenges they have faced. We will then ask a random sample of participants to engage in a randomized trial of these top-rated apps for 4 weeks. Apps will be rated on usability, acceptability, feasibility and effectiveness. Results from this trial will be quickly disseminated through several avenues: (1) the UWAC website and ALACRITY Centers network; (2) through CREATIV Lab's partnership with Mental Health America; (3) through the UW Center for Suicide Prevention and Recovery (CSPAR) and partnerships with other suicide focused organizations including Forefront, the American Foundation for Suicide Prevention, that American Association of Suicidology, the Rocky Mountain MIRECC, and the Defense Suicide Prevention Office and (4) through local partnership with King County and WA state contact tracers.

Aim 1: To determine the acceptability, feasibility, usability and effectiveness of mobile mental health apps for addressing risk factors associated with suicide risk in essential workers and unemployed individuals and to disseminate findings.

Question 1: Which mental health apps will be deemed to be acceptable (Acceptability of Intervention Measure), Feasible (Intervention Feasibility Measure), and Usable (Intervention Usability Measure) by essential workers and the unemployed?

Question 2: What features of these interventions did participants find particularly helpful?

Question 3: Which apps result in reduced depression (PHQ-9), anxiety (GAD-7) and better emotional regulation (DERS)?

Aim 2: To disseminate our findings and recommendations through national partnerships, the UWAC website, the ALACRITY Centers network, CSPAR and suicide prevention organizations, and WA state DPH.

Methods

Participants. Participants will be recruited in three ways: (1) mTurk; (2) MHA ads; and (3) Facebook Ads. We will aim to recruit 2,000 participants over the course of one week. Based on our past research, this sample is feasible to recruit in our proposed time frame. We have been able to recruit samples larger than this in 3 weeks using all of these methods. Participants will be eligible if (1) they are an essential worker or unemployed due to COVID19; (2) they have a past history of mental health issues or experiencing suicide ideation motivational risk factors based on the Integrated Motivational-Volitional (IMV) Model of Suicidal Behaviour. Participants will be compensated for their participation in this study.

Procedures. Participants will first be asked questions about their mental health needs, challenges they face accessing care, and strategies they have used to manage their mental health. All participants will then be shown App Store descriptions of ten apps that have received the highest rating by PsyberGuide, a non-profit company that consistently rates existing apps for their safety, data privacy and user ratings. Participants will provide initial impressions on the acceptability and feasibility of using these apps. We will then ask participants if they would be willing to participate in a randomized trial to test these apps, with the aim of recruiting 1000 participants. Participants will be randomized (100 per group) to one of the ten apps. They will be asked to download their assigned app and use it for 4 weeks. We selected four weeks because (1) this is ample time to determine the usability, acceptability and feasibility of these apps (2) based on past remote research, this is when we will see the first effects of apps on mental health outcomes and (3) also based on past research, this is the longest period of time we will be able to maintain a 100-80% of the

sample. After 4 weeks of use, participants will be asked to provide an evaluation of acceptability, feasibility and usability of the app, how often they used the app, and if they found the app helpful. They will also complete PHQ9, GAD7, and brief Difficulties with Emotion Regulation Scale (DERS) and four measures from the IMV model of suicidal behavior – defeat, entrapment, thwarted belongingness, and perceived burdensomeness. The Suicidal Behaviors Questionnaire-Revised (SBQ-R), a four-item self-report that assesses suicide attempts, ideation, communication, and intent since the last assessment. Given some limitations of the attempt item in the SBQ-R (which is combined with suicidal ideation), an additional item "Have you attempted to kill yourself?" will be added. This single-item has been demonstrated to identify a research rated suicide attempt in 89.3% of cases. We will also ask if they used any other mental health apps or services during this 4-week period.

Our findings will be rapidly complied and disseminated through the UWAC website and ALACRITY Centers network, through CREATIV Lab's partnership with Mental Health America; UW Center for Suicide Prevention and Recovery (CSPAR) and partnerships with other suicide focused organizations including Forefront, the American Foundation for Suicide Prevention, and that American Association of Suicidology, the Rocky Mountain MIRECC, and the Defense Suicide Prevention Office. We have also begun discussions with King County and WA state contact tracer training sites to determine the best means of distributing this information directly to people identified as exposed to C19.

Analysis

T-tests and chi-square tests will compare demographic and baseline clinical outcomes by missing data status at follow-up timepoint. Chi-square tests will examine the association between condition assignment and compliance (whether a participant used the app they were assigned to or used an alternative app). All analyses are intent-to-treat. Sensitivity analyses will be conducted excluding those who never downloaded or used the app they were assigned. Analyses of variance will be used to compare conditions on AIM, IAM, and IUS scores at follow-up. A series of mixed effects models using restricted maximum likelihood estimation will be built to test linear time change on the PHQ-9, GAD-7, and DERS-SF, and to test for condition differences at follow-up and change slope. Models will be built in an outwardly nested fashion, such that an initial null model was computed, followed by models that add a random intercept, random time component, condition assignment, and condition x time interaction effects. To test whether there was a dose-response relationship such that the app use frequency was associated with rate of change on PHQ-9, GAD-7, and DERS-SF scores, we will compute another series of mixed effects models for each outcome. An initial model will include variables for time and frequency of use, a second model will add condition terms for each app using Beautiful Mind as reference, a third model will add condition x frequency interaction terms for each app, and the fourth model will include time, frequency, and a time x frequency interaction term. Model comparisons will apply -2 Log Likelihood, Akaike Information Criterion, and Bayesian Information deviance statistics. To test the impact of app use frequency on change over time, similar nested model testing will be applied using an initial null model, followed by models that added dosage, dosage x time interaction, and condition assignment.

Sample Size and Power. A priori power analysis for an ANOVA *F* test indicated that a sample size of 1,000 (n=200 participants in each of the active and control app conditions) would be sufficient with a power of .80 and an alpha of .05 for a minimum detectable effect size (MDES) of Cohen's d=.24 for main effect comparisons between any two conditions.

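### Question 3 asks whether each app lowers symptoms, but with every participant given an app and no defined control, the design supports only comparisons between apps

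*Combined protocol and SAP*

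**What the plan says.** Aim 1, Question 3 sets the effectiveness question: "Which apps result in reduced depression (PHQ-9), anxiety (GAD-7) and better emotional regulation (DERS". It names no comparator.

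Methods, Procedures, gives the allocation: "Participants will be randomized (100 per group) to one of the ten apps". All ten are the apps rated highest by PsyberGuide. Use of other apps or services is recorded at 4 weeks, but no group is assigned to go without an app.

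The Analysis section says that mixed models will be built "to test linear time change on the PHQ-9, GAD-7, and DERS-SF, and to test for condition differences at follow-up and change slope". The models are nested, adding in turn a "random intercept, random time component, condition assignment, and condition x time interaction effects". A separate set of dose-response models names a reference app: "a second model will add condition terms for each app using Beautiful Mind as reference".

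Sample Size and Power describes 1,000 participants with "n=200 participants in each of the active and control app conditions". No section says which app is the control, whether it is expected to be inert, or which model term answers Question 3.

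**The concern.** Question 3 as worded calls for a comparison with what would have happened without the app. No arm described in the Procedures supplies it. A fall in score over 4 weeks, within one app or pooled over all, mixes any app effect with natural recovery, regression to the mean and changing pandemic conditions.

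The plan lists time change as a test in its own right and gives no rule for interpreting it. The awkward result is easy to foresee: a clear time slope with no detectable difference between apps. That could mean that all the apps help equally or that none does, and the data could not tell these apart. Aim 2 commits to rapid dissemination to suicide-prevention organisations and public-health partners, so a loose reading of the time slope would have an audience.

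**Working it through.** **1. Arms.** Procedures: 10 groups × 100 = 1,000, so the ten apps use the whole trial sample. Sample Size and Power: 1,000 / 200 = 5 conditions, at least one of them a control. The two descriptions do not match, and the control cannot be placed in either.

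**2. What each planned term estimates.** Write the mean change in app *j* as drift + effect*j*, where drift is the change expected with no app.

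- Pooled time slope: drift + average effect. Drift does not cancel.
- Change within app *j* (time plus that app's interaction term): drift + effect*j*. Drift does not cancel.
- Condition × time, app *j* against app *k*: effect*j* − effect*k*. Randomisation gives both arms the same expected drift, so it cancels, provided that dropout does not differ in a way that biases the contrast.
- Condition difference at follow-up: also effect*j* − effect*k*, because randomisation balances baseline in expectation.

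The last two identify differences only. To obtain effect*j* itself, one comparator would need a known effect of zero, and the documents do not say that any app has this.

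**3. Sensitivity of the protected contrasts.** The plan's own figure is d = 0.24 between any two conditions, at power 0.80 and alpha 0.05 (taken as two-sided; not stated). MDES = (1.960 + 0.842) × √(2/n).

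- n = 200: 2.802 × 0.100 = 0.280; power at d = 0.24 is 67%.
- n = 100: 2.802 × 0.1414 = 0.396; power at d = 0.24 is 40%.

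So 0.24 is not reproduced from the stated inputs. A baseline-adjusted comparison with an assumed correlation of 0.5 at n = 200 comes close: 0.280 × √(1 − 0.25) = 0.243. This shortfall is a separate matter. It matters here because a null between-app result beside a significant time slope is quite possible.

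**4. How often drift alone would look significant.** None of these inputs is in the documents: mean entry score *e* SD above the mean of the population from which participants come; pre-post correlation *r* of 0.7 to 0.8; no app effect; two-sided 0.05. Expected drop = (1 − r) × e. SE of mean change = √(2(1 − r)/n). For example, with e = 0.2 and r = 0.8 the drop is 0.04, the SE at n = 100 is 0.0632, the ratio is 0.63, and the probability is 10%.

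| e (SD) | Drop (SD), r = 0.8 to 0.7 | One app, n = 100 | Pooled, n = 1,000 |
|---|---|---|---|
| 0 | 0 | 5% | 5% |
| 0.1 | 0.02 to 0.03 | 6% to 7% | 17% to 23% |
| 0.2 | 0.04 to 0.06 | 10% to 12% | 52% to 69% |
| 0.5 | 0.10 to 0.15 | 35% to 49% | over 99% |
| 1.0 | 0.20 to 0.30 | 89% to 97% | over 99% |

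With 80 completers per app, the low end of the Procedures' retention range, the 35% becomes 29%. The table covers regression to the mean only; recovery or secular change would add to the drop or offset it. A correctly specified condition × time test stays at about 5% throughout, because the drift is shared.

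**The case against.** The strongest reply is that the protected analysis is already planned. The sentence that introduces time change goes on to condition differences at follow-up and in slope, and the final nested model contains condition × time. This stands. It would be wrong to infer that the plan relies on a time test alone. What is missing is a statement of which term answers Question 3, together with a question that those terms can answer.

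A reader might also infer that natural recovery will be reported as app effectiveness. The documents do not support that: they contain no rule that turns a significant time slope into a positive answer, and a pooled slope could not say which app works. The most that can be said is that the plan leaves this reading open.

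Nor do the documents support a claim that drift will be large. Eligibility sets no PHQ-9 or GAD-7 cutoff and accepts a past history alone, so entry elevation may be small or absent, and scores might even worsen during the crisis. The plan also specifies no separate pre-post test for each app, so the one-app column above illustrates a possible reading and not a planned analysis.

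Finally, the power text mentions a control app, and the dose-response models use Beautiful Mind as reference. Either could serve as a concurrent comparator. But the control is unnamed, the reference app is not called a control, and neither is described as inert. Naming one would sharpen the relative claim without making it absolute.

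**Conclusion.** The concern holds in this form: Question 3 as worded is not identified by the design described, and the plan does not say which of its tests answers it. The planned between-condition tests are sound for relative claims. The time slope is an uncontrolled pre-post change and cannot carry a claim of effectiveness.

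The structural conclusion needs no numerical assumption; it follows from allocating everyone to an app with no defined inert comparator. The size of the risk does depend on assumptions. With no app effect, the chance of a significant time change runs from the nominal 5% to 97% for one app and from 5% to over 99% pooled, according to an entry elevation that the documents do not give. No single value in that range should be quoted as the expected one.

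**What to change.** - In the Analysis section, state that Question 3 is answered by the between-condition contrasts already planned: condition differences at follow-up and condition × time.
- Reword Question 3 to ask which apps result in greater reduction than the other apps or the designated comparator.
- State that pooled and within-app time change will be reported as descriptive and will not be called effectiveness, including in the material disseminated under Aim 2.
- Reconcile the ten groups of 100 in the Procedures with the 200 per condition in Sample Size and Power. Then state whether Beautiful Mind or another app is the control, and what it is assumed to do. Remove the word control only if no such condition exists; if there is one, deleting the word would discard the design's one possible common comparator.

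These are wording changes to Aim 1, Procedures, Analysis and Sample Size and Power. They need no new arm, data or participants. The cost is a narrower permitted claim: the trial could say which apps do better than others, but not that any app works compared with no app.

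### Impressions of all ten apps are collected before randomisation but not used in the follow-up rating ANOVA, which may give up precision at almost no saving

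*Combined protocol and SAP*

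**What the plan says.** The Procedures subsection fixes the order of events. First, "All participants will then be shown App Store descriptions of ten apps", and "Participants will provide initial impressions on the acceptability and feasibility of using these apps". Only afterwards comes the invitation to the trial: "We will then ask participants if they would be willing to participate in a randomized trial to test these apps". After four weeks, "participants will be asked to provide an evaluation of acceptability, feasibility and usability of the app".

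The Analysis section gives one between-app analysis of these ratings: "Analyses of variance will be used to compare conditions on AIM, IAM, and IUS scores at follow-up". No covariate is named, and no use of the initial impressions is described anywhere. By contrast, PHQ-9, GAD-7 and DERS-SF are given mixed models of change over time.

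Three things are left open. No instrument or scoring is named for the initial impressions. They cover acceptability and feasibility but not usability. And the Analysis section does not define IAM, whereas Question 1 under Aim 1 names an Intervention Feasibility Measure; I take IAM to be the feasibility score, so only AIM matches a baseline domain beyond doubt.

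**The concern.** Question 1 under Aim 1 asks which apps are acceptable, feasible and usable, so it is an app-versus-app question, and this ANOVA is what answers it. Some people tend to rate everything high and others everything low. In an unadjusted comparison that variation stays in the residual and widens every interval between apps.

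The plan already asks each participant, before assignment, for a reaction to all ten apps. A summary of those reactions is a natural measure of rating habit. If it predicts the follow-up rating, leaving it out discards precision in a trial that may have only 100 people per app.

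**Working it through.** **Inputs**

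- Group size: Procedures says "Participants will be randomized (100 per group) to one of the ten apps". Sample Size and Power says "a sample size of 1,000 (n=200 participants in each of the active and control app conditions", which implies 1,000/200 = 5 conditions. Both sizes are carried below.
- Retention: Procedures expects 80% to 100% at four weeks, so as few as 0.80 × 100 = 80 analysed per app.
- Error rates: "with a power of .80 and an alpha of .05". Sidedness is not stated; two-sided is assumed, with no multiplicity adjustment.
- Correlation r between the ten-app mean impression and the follow-up rating: not in the documents. Assumed range 0 to .6.

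**Step 1: the plan's own figure.** The unadjusted pairwise detectable difference in SD units is d = (1.960 + 0.842) × √(2/n).

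- n=200: 2.802 × √(2/200) = .280. The plan states .24, which is not reproduced; a one-sided test gives (1.645 + 0.842) × 0.100 = .249.
- n=100: 2.802 × √(2/100) = .396.
- n=80: 2.802 × √(2/80) = .443.

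**Step 2: the effect of adjustment.** A covariate independent of assignment and correlated r with the outcome multiplies the residual variance by 1 − r², so d is multiplied by √(1 − r²). Equivalent group size is n/(1 − r²).

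| r | 1 − r² | SE reduction | d, n=100 | 100 behaves like | d, n=80 | d, n=200 |
|---|---|---|---|---|---|---|
| 0 | 1.00 | 0% | .396 | 100 | .443 | .280 |
| .1 | .99 | 0.5% | .394 | 101 | .441 | .279 |
| .3 | .91 | 4.6% | .378 | 110 | .423 | .267 |
| .5 | .75 | 13.4% | .343 | 133 | .384 | .243 |
| .6 | .64 | 20.0% | .317 | 156 | .354 | .224 |

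**Step 3: the cost if r is near zero.** With ten arms of 100 the residual degrees of freedom are 1,000 − 10 = 990; one covariate takes one. At 80% retention they are 800 − 10 = 790, again less one.

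**Step 4: which covariate.** The mean over all ten apps is fixed before randomisation and is the same whichever app is assigned, so its expected value is equal across arms and it does not bias the app contrasts. The raw initial rating of the assigned app is different, because its arm average varies with the prior appeal of the app. Adjusting for it shifts each contrast by slope × difference in mean prior appeal. As an illustration with assumed values, a slope of 0.5 and an appeal difference of 0.3 SD move the contrast by 0.5 × 0.3 = 0.15 SD. Part of a real difference in acceptability would be taken out, and the question would become acceptability net of first impression.

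**The case against.** The strongest reply is that nothing here is an error. An unadjusted ANOVA on randomised arms is valid, and the plan does not contradict itself on this point. That stands: this is a gain in efficiency, not a correction.

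A second reply is that the benefit is assumed. The covariate would be a mean reaction to ten store descriptions, nine of them for apps the person is not assigned, while the outcome is a rating of one app after four weeks. A low r is plausible, and at r=.1 the standard error falls by only 0.5%. This also stands, and it is why the table starts at zero. It is not a reason against the change, since at low r the loss is one degree of freedom in about 990.

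Third, the text speaks of impressions and names no scale, so a reader who infers that usable baseline scores already exist goes beyond the documents. The impressions could be rankings or free text. This stands and shapes the fix.

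Fourth, usability has no baseline counterpart. A covariate need only precede randomisation and be prognostic, so the other two means may still be used, but with no presumption of gain.

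A reader might also infer that any baseline rating can be adjusted for without bias. Step 4 shows that this fails for the raw rating of the assigned app.

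**Conclusion.** The point holds as a low-cost improvement. The plan asks for pre-randomisation impressions of all ten apps and does not use them in the comparison that answers Question 1. Adjusting for the ten-app mean would leave the app contrasts unbiased and would bring the pairwise detectable d at 100 per app from about .40 to between .39 (r=.1) and .32 (r=.6). With 80 analysed per app, it would go from .44 to .38 at r=.5. The gain is negligible at low r and material from about r=.5.

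These figures rest on an assumed r, a two-sided .05 test, 80% power and impressions that are scored numerically. They apply to acceptability and feasibility only.

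Two stronger readings are not supported. The documents do not show that precision is certainly being lost, because r is unknown. Nor would adjustment restore the planned sensitivity: at 100 per app even r=.6 leaves d at .317, above the stated .24. The conflict between 100 per group and 200 per condition is a separate and larger power problem, and it must be reconciled in its own right.

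**What to change.** 1. In Procedures, state that the initial impressions of acceptability and feasibility are recorded as numeric scores for each of the ten apps, and name the items and scoring.
2. In Analysis, replace the ANOVA with ANCOVA. Use each participant's mean initial acceptability over all ten apps as covariate for acceptability, and the mean initial feasibility for feasibility.
3. For usability, the average of the two means may be used, with no gain assumed.
4. State that the raw initial rating of the assigned app will not be a covariate. If an app-specific term is wanted in addition, use the participant's rating of that app minus the app's average over all survey respondents.

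The cost is a few sentences and one degree of freedom per model. No extra visit or participant is needed. If the impressions are not already scored, the survey wording must be settled before recruitment.

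### Recruitment channel and target group enter no outcome model, so the condition-only comparison of app ratings forgoes a small, nearly free gain in precision and some protection against uneven dropout

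*Combined protocol and SAP*

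**What the plan says.** Methods, Participants names the channels: "Participants will be recruited in three ways: (1) mTurk; (2) MHA ads; and (3) Facebook Ads". The first eligibility criterion defines the target groups: "they are an essential worker or unemployed due to COVID19". Methods, Procedures gives one sentence on allocation: "Participants will be randomized (100 per group) to one of the ten apps". It neither describes nor rules out a sequence method, blocking or stratification. The same paragraph justifies the four-week period partly by expected retention ("this is the longest period of time we will be able to maintain a 100-80% of the" sample).

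For the ratings, the Analysis section states: "Analyses of variance will be used to compare conditions on AIM, IAM, and IUS scores at follow-up". Condition is the only term. The mixed models for PHQ-9, GAD-7 and DERS-SF contain a random intercept, time, condition, frequency or dosage of use, and interactions among these. Channel and target group appear in none of them. Demographic and baseline clinical variables have one stated use, a comparison of participants with and without follow-up data.

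Sample Size and Power uses a different layout, "a sample size of 1,000 (n=200 participants in each of the active and control app conditions", which implies five arms rather than ten.

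**The concern.** Target group is an eligibility criterion, and channel follows from the route by which a person arrived. Neither can be affected by the assigned app, so both are legitimate covariates. If they predict how people rate an app, leaving them out makes every between-app comparison less precise than it need be.

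The second issue is missing ratings. AIM, IAM and IUS are compared at follow-up, and no missing-data method is stated for them. If people in one group drop out more from some apps than from others, the completers in those arms have a different mix, and an unadjusted comparison of means carries that difference. The plan checks which variables go with missingness but does not carry the result into any model.

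The results are meant to tell essential workers and the unemployed which apps to use, so a cheap gain in the reliability of the comparisons is worth having.

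**Working it through.** **Inputs from the documents.** Ten arms of 100 (Procedures); 200 per arm at N=1,000 (Sample Size and Power); alpha .05 and power .80 ("would be sufficient with a power of .80 and an alpha of .05"); target effect "Cohen's d=.24 for main effect comparisons between any two conditions"; retention 80% to 100%. Tests are taken as two-sided, because sidedness is not stated.

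**Inputs assumed.** Channel shares, the split between target groups, and the R-squared of these factors with the outcomes are not given. Shares of 20%, 33% and 50% and an R-squared of 1% to 10% are used.

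**1. The plan's own figure.** Pairwise MDES = (1.960 + 0.842) × sqrt(2/n), with SD = 1.
- n=200: 2.802 × 0.1000 = .280, and power at d=.24 is 67.0%. The stated .24 is not reproduced; it would need 273 per arm.
- n=100: 2.802 × 0.1414 = .396, and power at d=.24 is 39.6%.

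**2. What R-squared is plausible.** For three equal channels with means −g/2, 0 and g/2, R-squared = (g²/6)/(1 + g²/6).
- g=.3: .015/1.015 = .015
- g=.5: .0417/1.0417 = .04
- g=.8: .1067/1.1067 = .096

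The top of the assumed range therefore needs a gap of about .8 SD between the extreme channels.

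**3. Gain from adjustment.** Adjusted MDES = MDES × sqrt(1 − R²); equivalent n = n/(1 − R²).

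| R² | MDES, 100 per arm | Power at d=.24, 100 per arm | Equivalent n | MDES, 80 per arm |
|---|---|---|---|---|
| 0 | .396 | 39.6% | 100 | .443 |
| 1% | .394 | 40.0% | 101 | .441 |
| 2% | .392 | 40.3% | 102 | .439 |
| 5% | .386 | 41.3% | 105 | .432 |
| 10% | .376 | 43.2% | 111 | .420 |

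At 200 per arm the same factor takes .280 to .280 × sqrt(.99) = .279 and .280 × sqrt(.90) = .266.

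**4. Chance imbalance in mix.** Under simple randomisation, the SD of the difference in share between two arms is sqrt(2p(1−p)/n). At n=100 this is 7.1 points for p=.5 and 6.7 for p=1/3. By simulation, the gap between the highest and lowest of ten arms of 100 averages 15 points for p=.5, 14 for p=1/3 and 12 for p=.2. With five arms of 200 it averages about 8 points for p=1/3 or .5.

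**5. What that imbalance does to arm means.** With three equal channels and g of .3, .5 and .8 SD, channel mix alone spreads the best and worst of ten arm means by .04, .06 and .10 SD on average. The total chance spread among ten identical arms of 100 is about .31 SD. Removing channel entirely lowers it to .306, .302 and .293.

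**6. Uneven dropout (hypothetical).** Suppose an arm split 50:50 loses 40% of one half and none of the other. It keeps 30 + 50 = 80 people, and the depleted group's share falls from 50% to 30/80 = 37.5%, a shift of 12.5 points. Against a comparator that loses nobody, the bias is .125 × .3 = .04 SD if the groups differ by .3 SD, and .125 × .8 = .10 SD if they differ by .8 SD. The target effect is .24. Including the group in the model removes this bias when dropout depends only on app and group and the group difference in ratings is similar across apps.

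**The case against.** A reader might infer that the trial is unstratified, that the channels bring in very different people, and that imbalance of 14 to 15 points between extreme arms will mislead the choice of best and worst app. The documents do not support this reading. They are silent on the allocation method, so one can say only that stratification is not described. They report no difference in severity, engagement or dropout by channel. Chance imbalance under valid randomisation is not bias, and the standard errors already include it. Step 5 shows that nearly all of the chance spread among arms remains after channel is removed.

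The precision gain is also small, and it depends on an R-squared that nobody has supplied. For PHQ-9, GAD-7 and DERS-SF, the random intercept already absorbs stable differences between people. With complete data at both times, a main-effect covariate leaves the condition × time estimate essentially unchanged; only a covariate that predicts change can help there. The dropout argument is conditional as well, since nothing in the documents shows that dropout varies by app and group together.

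All of this stands, and it sets the size of the point. What remains is that the rating ANOVAs have no random intercept, no covariates and no stated handling of missing ratings, and that adjusting them costs almost nothing.

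**Conclusion.** The point holds as a minor improvement. Two variables that can be known before randomisation are absent from every outcome model, and the effect falls mainly on the AIM, IAM and IUS comparisons. For an assumed R-squared of 1% to 10%, adjustment is worth the equivalent of 1 to 11 participants per arm of 100 and adds 0.3 to 3.6 percentage points of power at d=.24. It also guards against a bias of perhaps .04 to .10 SD under the dropout pattern in step 6, which is an illustration and not a forecast.

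These figures use ten arms of 100. The 200 per arm in Sample Size and Power conflicts with that, and the two sections must be reconciled. That conflict is the larger problem: unadjusted power at d=.24 is about 40% at 100 per arm and 67% at 200, against the stated 80%. Covariate adjustment does not repair it.

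**What to change.** Record the recruitment channel for each participant. Prespecify channel and target group as covariates in the AIM, IAM and IUS analyses, with ANCOVA in place of ANOVA. Add both, with their time interactions, to the PHQ-9, GAD-7 and DERS-SF mixed models. State the allocation method in Procedures.

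The cost is SAP wording and, in each rating analysis, two degrees of freedom for channel and one for target group, out of about 1,000. The time interactions use three more in each mixed model.

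Blocking within channel and target group is optional, because adjustment alone recovers nearly all the gain. Showing app means by target group is also optional; it would suit Question 1, but at an assumed 50:50 split each cell would hold only about 50 people. Adding further demographic covariates is not asked for, since the documents do not list them.
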